### 11.2.2 SECONDARY OBJECTIVES

Immune activation markers will be graphically displayed at baseline (pre-treatment) and at time of surgical resection, and summary statistics will be reported for baseline, follow-up and changes over time. Based on our prior studies a 50% increase in immune stimulatory cytokines and 50% decrease in Treg levels is anticipated.

Transformations will be taken as needed (e.g. log transform) to adhere to assumption of statistical methods. Comparisons of baseline vs. follow-up measures will be made using paired t-tests. Logistic regression will be used to evaluate the association between baseline immune markers and clinical response and to evaluate associations between changes in immune markers and response. Both absolute change and percentage change in markers will be considered

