### **3.4 STUDY RATIONALE**

Our past clinical trials with HNSCC patients have shown the feasibility of pre-surgical targeted or immunotherapy followed by multi-modality treatments combining surgery and adjuvant therapy leading to an improvement in recurrence free survival [35-37]. A similar multi-modality treatment is being proposed in this application to overcome immune lethargy by Nivolumab treatment to block PD 1 between the time of OCSCC diagnosis and surgical treatment. This duration of time will allow for the administration of three doses of Nivolumab given on Days 1, 15 and 29. The primary objective of the proposed study is to determine the efficacy of neoadjuvant PD-1 inhibition in patients with oral cavity cancer undergoing definitive surgical resection. In addition to assessing the clinical efficacy of Nivolumab, secondary objectives will be to analyze the effectiveness of PD-1 antibodies at

restoring the immune reactivity in the peripheral blood as well as stimulating intratumoral immune activity. The rationale for this approach is based on the overexpression of lymphoid PD 1 in the HNSCC environment along with our prior demonstration of the feasibility of pre-surgical immune modulatory treatment or targeted mTOR therapy having positive post-surgical clinical effectiveness [30, 35, 36, 38]. Additionally, blocking PD 1 prior to surgical excision will allow restoration of immune competence to not only enable pre surgical immune responsiveness to HNSCC, but also post-surgical immunological surveillance for residual cancer.

We hypothesize 25-30% overall response rate (PR+CR) in patients with OSCC, and these patients will reveal a systemic and intratumoral response following anti-PD-1 therapy along with immune reactivity to autologous OCSCC.

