#### **11.1.3 EVALUABLE FOR IMMUNE ACTIVATION AND REACTIVITY**

Patients who have received at least two doses of nivolumab and have both a pre-treatment and a post-treatment sample available for measuring immune markers will be included in the analyses for the secondary objectives of the study.

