### 11.3 DETERMINATION OF SAMPLE SIZE

This study will enroll up to 19 patients. The Simon two-stage design is based on a total of 17 patients who are evaluable for efficacy. We may enroll up to 19 to allow for up to two patients to be inevaluable.

Without treatment, the rate of response would be expected to be very low (<2%). With treatment, we anticipate a meaningful pathological response rate of 25%. Using a Simon optimal two-stage design with alpha of 4% and power of 91%, we can detect this difference with a sample size of no more than 17 patients. In stage 1, 9 patients will be enrolled. If none respond, the study will be stopped. If one or more responds, we will continue to the 2nd stage and an additional 8 patients will be enrolled. If a total of 2 or more patients respond out of 17 we will reject the null hypothesis and conclude that treatment with Nivolumab results in a meaningful pathological response for patients with HNSCC.

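### Section 11.2.2 plans logistic regression of response on immune markers with about 4 responders expected among 17 patients, but names no estimator or test that works at such counts

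*Combined protocol and SAP*

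**What the plan says.** Section 11.2.2 of the combined protocol and SAP states: "Logistic regression will be used to evaluate the association between baseline immune markers and clinical response". The same sentence extends the method to associations between changes in markers and response, and the section adds: "Both absolute change and percentage change in markers will be considered". The only provision for model assumptions is "Transformations will be taken as needed (e.g. log transform) to adhere to assumption of statistical methods". No estimator (maximum likelihood, penalized or exact), test, significance level, separation rule or limit on covariates is given.

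On numbers, Section 11.3 states: "The Simon two-stage design is based on a total of 17 patients who are evaluable for efficacy". On the rate, it says "With treatment, we anticipate a meaningful pathological response rate of 25" percent. Section 3.4 has: "We hypothesize 25-30% overall response rate (PR+CR) in patients with OSCC". Section 11.1.3 restricts the marker analyses to "Patients who have received at least two doses of nivolumab and have both a pre-treatment and a post-treatment sample available for measuring immune markers", so the marker sample can be smaller than 17.

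The outcome is also unclear. Section 11.2.2 first calls it clinical response and then just response. Section 11.2.1 lists clinical, radiographic and pathologic response rates separately. Section 11.5 words the stage 1 stopping rule in terms of clinical response, where Section 11.2.1 words it in terms of pathologic response.

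**The concern.** These two regressions are the only planned analyses that link markers to response, and the smaller outcome group will probably hold two to five patients. Maximum-likelihood logistic regression behaves badly at such counts, in two ways.

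If every responder's marker value lies beyond every non-responder's (complete separation), no finite odds ratio exists. As the data approach separation, the standard error of the slope grows faster than the slope, so the Wald statistic shrinks as the marker gets stronger. A strong marker can then be reported as non-significant or non-estimable. The ordinary likelihood-ratio test avoids the loss of power, but it rejects too often under the null and still leaves an infinite estimate when the data separate.

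Transforming the marker does not help. A monotone transformation leaves complete separation in place, and the number of responders is unchanged.

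**Working it through.** **1. The plan's own design.** Inputs are from Sections 11.2.1 and 11.3: stage 1 n = 9, stop at 0 responders; total n = 17, reject at 2 or more; null rate 2%, alternative 25%.

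P(reject) = 1 − (1−p)^9 − [9p(1−p)^8](1−p)^8.
- p = 0.02: 1 − 0.8337 − 0.1531 × 0.8508 = 0.036 (stated 4%).
- p = 0.25: 1 − 0.0751 − 0.2253 × 0.1001 = 0.902 (stated 91%).

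The design reproduces to within a percentage point, so N = 17 is a sound starting point.

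**2. How many responders the regressions will have.** Expected number at 25%: 17 × 0.25 = 4.25. Given that stage 2 is reached:

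| Rate | Mean | P(1) | P(2-5) | P(6 or more) |
|---|---|---|---|---|
| 25% | 4.4 | 2% | 72% | 25% |
| 30% | 5.2 | 1% | 57% | 42% |

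These use the pathological rate, because the documents give no rate for clinical response.

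**3. Behaviour of the tests.** These inputs are assumptions, not figures from the documents: two-sided 5%, one marker per model, a normal marker with SD 1, and responders shifted by 0, 1, 1.5 or 2 SD. N is 17 and the number of responders R is held fixed.
- Wald: z = b/SE(b), counted as non-significant under separation.
- Likelihood ratio (LR): 2(l1 − l0).
- Firth: maximise l + ½ log|I|, where I is the information matrix, and test with twice the difference in that penalized log-likelihood with the slope free and with it fixed at 0.
- Rank-sum: exact p-value.

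Power in %, at 1 / 1.5 / 2 SD (2,000 simulated trials per cell):

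| R | Wald | LR | Firth penalized LR | Exact rank-sum | Complete separation |
|---|---|---|---|---|---|
| 2 | 0 / 0 / 0 | 32 / 56 / 77 | 20 / 40 / 64 | 15 / 32 / 54 | 9 / 20 / 38 |
| 3 | 1 / 1 / 2 | 38 / 68 / 88 | 28 / 55 / 81 | 28 / 56 / 78 | 5 / 13 / 30 |
| 4 | 4 / 10 / 11 | 44 / 75 / 93 | 33 / 66 / 88 | 32 / 63 / 85 | 2 / 8 / 23 |
| 5 | 11 / 22 / 24 | 48 / 81 / 96 | 39 / 73 / 92 | 38 / 73 / 92 | 1 / 7 / 18 |

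Repeat runs moved single cells by about 2 points; one put Firth at 19-38% for 1 SD and 66-93% for 2 SD. At R = 6 Wald power is still only 36% at 2 SD.

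Type I error over R = 2-5, nominal 5%: Wald 0.0-1.1%; LR 6.3-8.3% (8.1-9.9% with a log-normal marker); Firth penalized LR 3.5-4.8% (2.7-3.3% log-normal); exact rank-sum 3.0-5.1%.

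**4. The test matters as much as the estimator.** Averaged over R = 2-5 with Binomial(17, 0.25) weights, power at 1 / 1.5 / 2 SD is 31 / 61 / 84% for Firth with the penalized LR test. For Firth with a Wald test it is 3 / 10 / 20%.

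**5. What the remedy gives up.** If the ordinary LR test is recalibrated to a true 5%, its power at 1 SD is 23, 31, 37 and 42% for R = 2-5. Firth at its nominal cutoff gives 18, 27, 35 and 37% in the same run, a loss of about 2-6 points. The smallest two-sided rank-sum p-value is 2/17 = 0.118 with one responder and 2/136 = 0.015 with two.

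**6. Multiplicity.** With k independent null tests at 5%, P(any false positive) = 1 − 0.95^k, which is 40% for k = 10 and 64% for k = 20. Section 10.2 lists 1 + 4 + 5 + 4 = 14 measurements (Treg, activation, tumour cytokine, reactivity) before absolute and percentage changes are counted separately.

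**The case against.** The strongest reply is that the plan says only logistic regression. It does not commit to maximum likelihood, to Wald or to the likelihood ratio, and Firth and exact conditional methods are also logistic regression. That stands. A reader might infer that the plan has chosen a failing test, but the documents show an omission. The omission still matters, because both ordinary choices perform poorly here and the choice would be made after the data are seen.

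A reader might also infer that many markers will enter one model. Nothing in the documents proposes this.

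It can be said that the association is not a listed objective: Section 2.2 concerns immune activation and reactivity, which the graphs, summaries and paired t-tests address. That also stands and limits the weight of the point, although the hypothesis in Section 3.4 does tie immune changes to responding patients. Neither the primary endpoint nor any stopping rule depends on these regressions.

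The inflation of the LR test is moderate and smaller than the multiplicity problem. That is correct; the Wald failure and the non-estimable odds ratios carry the case.

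Finally, there may be six or more responders, and the counts borrow the pathological rate for an outcome called clinical response. Both caveats stand. The first softens the conclusion without reversing it, since Wald remains weak at six.

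**Conclusion.** The point holds as an unspecified method in a setting where the default is unfit. At 2-5 responders among 17, Wald power is 0 to about 11% at a 1 SD shift and 0-24% at 2 SD. Complete separation affects about 20-40% of datasets at 2 SD, and the ordinary likelihood-ratio test runs at about 6-8%, or up to 10% with a skewed marker. Firth with the penalized likelihood-ratio test keeps type I error at or below the nominal level (about 4-5% with a normal marker) and has about 64-93% power at 2 SD.

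Two further inferences are not supported. The remedy does not make the analysis well powered: at 1 SD, Firth power is about 20-40%. Nor is it free, given the shrinkage and the small loss of power shown above.

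The power figures rest on the assumed 5% level, single normal marker and 1-2 SD shifts; the documents give no effect size for these regressions. If missing paired samples bring the marker population below 17, information falls further. This is a worthwhile, inexpensive improvement to a supporting analysis and does not affect the primary result.

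**What to change.** Replace the logistic regression sentence in Section 11.2.2 with text that:
- analyses each marker, and each marker change, one at a time;
- names Firth-penalized logistic regression with penalized likelihood-ratio p-values and profile penalized-likelihood intervals, and excludes Wald tests on the Firth fit; or else names the exact Wilcoxon rank-sum test;
- states whether the outcome is clinical or pathologic response, and uses that term consistently;
- labels these analyses exploratory.

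The cost is a sentence or two and standard software, with no extra patients or samples and no change to the primary analysis. Firth odds ratios are shrunk toward 1, and about 2-6 points of power are lost at 1 SD against a size-corrected likelihood-ratio test. The rank-sum test gives no odds ratio or covariate adjustment, is weaker than Firth at two responders (15% against 20% at 1 SD), and cannot reach 5% with one. Multiplicity across markers and across absolute and percentage change is not addressed and needs its own statement.

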### 11.3 DETERMINATION OF SAMPLE SIZE

This study will enroll up to 19 patients. The Simon two-stage design is based on a total of 17 patients who are evaluable for efficacy. We may enroll up to 19 to allow for up to two patients to be inevaluable.

Without treatment, the rate of response would be expected to be very low (<2%). With treatment, we anticipate a meaningful pathological response rate of 25%. Using a Simon optimal two-stage design with alpha of 4% and power of 91%, we can detect this difference with a sample size of no more than 17 patients. In stage 1, 9 patients will be enrolled. If none respond, the study will be stopped. If one or more responds, we will continue to the 2nd stage and an additional 8 patients will be enrolled. If a total of 2 or more patients respond out of 17 we will reject the null hypothesis and conclude that treatment with Nivolumab results in a meaningful pathological response for patients with HNSCC.

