### **3.3 IMMUNOTHERAPY IN HNSCC**

Because of the combination for the need of new therapies and the benefits of a neoadjuvant treatment strategy, the possibility of immunotherapeutic approaches for HNSCC patients has gained interest. Unfortunately, HNSCC patients have profound immune defects that are associated with a worse outcome and have been attributed to tumor production of inhibitory mediators and tumor-induced immune inhibitory cell populations [25-30]. Programmed Death receptor I (PD-1) and its ligand (PD-L1) appear to contribute to this immune dysfunction as 50-60% lymphocytes from HNSCC patients have upregulated PD-1 expression and PD-1 blockade enabled lymphocyte proliferative reactivity to stimulation and indirectly overcame immune unresponsiveness by modulating immune inhibitory populations, including T regulatory cells [30-33]. Furthermore, tumor PD-L1 expression has been associated with improved objective response and clinical benefit in multiple tumor types [34]. Since 60-80% of OCSCC express PD-L1, it is anticipated PD-1 blockade will benefit 20-25% of patients with OCSCC [30, 33, 34]. Most recently the Checkmate 141 Phase III trial revealed in patients with treatment-resistant and rapidly progressive head and neck carcinoma that nivolumab treatment was associated with an improved 12-month overall survival of 36%, compared with 17% in the Investigator Choice arm [40, 41].

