## 11.2 DATA ANALYSIS PLANS

### 11.2.1 PRIMARY OBJECTIVE

The clinical, radiographic and pathologic response rates will each be estimated with a 95% confidence interval, accounting for the two-stage design [41]. The null hypothesis is a 2% pathological response rate and the alternative is a 25% pathological response rate. If no patients respond in the first nine evaluable patients enrolled, the study will be terminated and we will conclude that there is not sufficient activity to reject the null hypothesis. The trial may pause enrollment after the first nine patients (if needed) to follow the ninth patient for a pathologic response. Note, however, that it is possible that an earlier patient may respond which would negate the need to stop enrollment (e.g. the 2nd patient may respond which would satisfy the criteria of at least one patient response in the first nine patients). If at least one patient has a pathologic response among the first nine evaluable patients enrolled, an additional eight patients will be enrolled. If two or more patients among 17 evaluable patients respond, we will reject the null hypothesis. The reported p-value will be based on two-stage design and any deviations from the intended sample size will be accounted for using the approach by Koyama and Chen [41]. Deviations from the planned sample size would only include the need for replacement patients in the event of a patient withdrawal following a single dose of Nivolumab secondary to toxicity or patient preference. If this were to occur these withdrawn patients would be excluded from the efficacy analysis. Only patients that receive at least 2 doses of Nivolumab will be included in the efficacy analysis. Briefly, Koyama and Chen's approach adjusts the final results of the Simon two-stage design (point estimate, 95% confidence interval, and p-value) by considering the evaluation of the data at the end of the 1st stage of the design. Ignoring the two-stage nature of the design, the estimated response rate (i.e. number of responders divided by the total number of patients at the end of stage 2) tends to underestimate the true response rate. In addition, the p-value and 95% confidence interval based simply on the maximum likelihood estimate using the total number of responses and total sample size will not be valid if the futility stopping evaluation is ignored. The approach for implementing the adjustment can be found here:

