### 11.4 SAFETY ANALYSIS

Adverse events occurring between enrollment and 6 weeks after surgery will be tabulated by type and grade. Adverse events that are at least possibly related to nivolumab will be tabulated separately.

Safety monitoring will occur continuously during the study. We anticipate nivolumab to be well-tolerated in this patient population and would anticipate a low ( $\leq 5\%$ ) rate of grade 3 and 4 adverse events that are at least possibly related to nivolumab. If there were strong evidence during the course of the trial that the rate of grade 3 and 4 adverse events was 25% or higher, we would stop the study. Using a likelihood-based approach, the study will stop if the likelihood ratio for a grade 3-4 AE rate of 25% vs. a grade 3-4 AE rate of 5% is 4 or higher. This is based on the binomial distribution. The stopping boundaries based on this approach are shown in the table below. Note that the upper limit on the sample size 19 due to the potential need to enroll up to 19 patients in the case of up to two patients inevaluable for response.

Stop the trial if:	Observed rate	Likelihood Ratio
2 of 3-9 pts have grade 3-4 AEs	22% - 67%	$\geq 4.78$
3 of 10-17 pts have grade 3-4 AEs	18% - 30%	$\geq 4.57$
4 of 18-19 pts have grade 3-4 AEs	21% - 22%	$\geq 4.36$

Additionally, if there is evidence that there is a delay in time to surgery due to adverse events, the study will be stopped. It would be considered acceptable if 5% or fewer of patients experienced a delay (i.e. greater than 3 weeks from their last dose of nivolumab.. A rate of delay of 10% or greater would be considered unacceptable. Given these assumptions and the use of a likelihood-based approaches as above (with a likelihood ratio of 4 or greater in favor of 20% causing study stoppage). The stopping boundaries are listed below:

Stop the trial if:	Observed rate	Likelihood Ratio
3 of 3-15 pts have a surgery delay	20% - 100%	$\geq 4.20$
4 of 9-19 pts have a surgery delay	21% - 25%	$\geq 7.11$

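### The 9+8 design has power 90.2%, not 91%, and at exactly 2 of 17 responses its one-sided test rejects 2% while the 95% interval still contains it

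*Combined protocol and SAP*

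**What the plan says.** - **Hypotheses (11.2.1).** "The null hypothesis is a 2% pathological response rate and the alternative is a 25% pathological response rate".
- **Design (11.3).** A Simon optimal two-stage design with "alpha of 4% and power of 91" (percent), with at most 17 evaluable patients. "In stage 1, 9 patients will be enrolled. If none respond, the study will be stopped". Otherwise eight more are enrolled, and the null is rejected at two or more responses in 17. The section does not say whether 4% and 91% are design limits or attained values, or whether alpha is one-sided. Enrolment may reach 19 to cover two inevaluable patients.
- **Estimation (11.2.1).** The response rates "will each be estimated with a 95% confidence interval, accounting for the two-stage design". The p-value and interval follow the Koyama-Chen method.
- **Safety stops (11.4).** Two tables stop the trial. The toxicity table begins "2 of 3-9 pts have grade 3-4 AEs" and goes on to 3 of 10-17 and 4 of 18-19. The surgery-delay table has 3 of 3-15 and 4 of 9-19. The anticipated rate of related grade 3-4 events is at most 5%, and a delay rate of at most 5% is acceptable. No section says how a trial stopped for safety enters the efficacy test.

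**The concern.** A reader who recomputes the printed rule obtains the stated alpha to the nearest percent but not the stated power, and the discrepancy flatters the design. The stated power also takes no account of the rules in 11.4, which can end the trial before 17 patients are evaluated.

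The second matter is the smallest positive result. The decision spends its whole error rate in one tail, while a 95% interval spends 2.5% in each. At 2 of 17 a report could say that 2% is rejected and also show an interval that contains 2%. Since sidedness is not stated, someone might also double the p-value (2 × 0.036 = 0.072) and question the declared success.

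**Working it through.** **Inputs.** From 11.2.1 and 11.3: p0 = 0.02, p1 = 0.25, stop at 0 of 9, reject at 2 or more of 17.

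**1. Alpha and power.** The null is not rejected if there are 0 responses in 9, or exactly 1 in the first 9 and none in the next 8. So

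P(reject | p) = 1 − (1−p)^9 − 9p(1−p)^16.

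- p = 0.02: 1 − 0.83375 − 0.13028 = 0.0360. This reproduces the stated 4%.
- p = 0.25: 1 − 0.07508 − 0.02255 = 0.9024. This rounds to 90%; 91 − 90.2 = 0.8 points.

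**2. Which limits the design meets.** An exhaustive search finds the 9+8 rule to be Simon-optimal for limits of 4%/90% and of 5%/90%. For 4%/91% the optimal design is instead 0 of 10, then 2 or more of 16 to reject (3.5%, 91.0%).

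**3. Test against interval.** At 2 of 17 the Koyama-Chen p-value equals P(reject | 0.02). The lower limits solve P(reject | p) = 0.025 or 0.05. Other counts follow the same method.

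| Responses in 17 | One-sided p | Lower 95% limit | Lower 90% limit | Rule |
|---|---|---|---|---|
| 1 | 0.166 | 0.28% | 0.57% | not rejected |
| 2 | 0.036 | 1.64% | 2.40% | rejected |
| 3 | 0.004 | 3.91% | 5.14% | rejected |
| 4 | 0.0003 | 6.86% | 8.53% | rejected |

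The 95% interval disagrees with the rule only at 2 of 17, where it runs from 1.6% to 38.5%. The 90% interval agrees at every count shown. To see how often this count arises: P(exactly 2 of 17, with at least one in stage 1) = (136 − 28)p²(1−p)^15. As a share of all rejections this is 0.0319/0.0360 = 89% at a true rate of 2%, 50% at 10%, and 0.0902/0.9024 = 10% at 25%.

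**4. Power with the safety stops.** This step needs assumptions that the plan does not make. Those used are: the printed tables; the second delay row read as 16-19, because its printed observed rates of 21-25% are 4/19 to 4/16; toxicity, delay and response mutually independent; 17 patients; true response rate 25%. At event rates of exactly 5%, the chance of stopping is 9.19% for toxicity and 3.65% for delay. If every stop counts as not positive, power is 0.9024 × 0.9081 × 0.9635, or 0.789 with unrounded factors.

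| Toxicity rate | Delay rate | Every stop counted as not positive | Stopped trial with two responses already seen counted as positive |
|---|---|---|---|
| 5% | 0 | 81.9% | 87.3% |
| 0 | 5% | 86.9% | not computed |
| 5% | 5% | 78.9% | 86.9% |
| 2% | 5% | 85.6% | not computed |
| 2.5% | 2.5% | 87.6% | not computed |

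**5. The delay rule.** The text of 11.4 calls 10% or more unacceptable but sets the likelihood ratio in favour of 20%. The printed ratios correspond to 10% against 5%: 3 of 15 gives 2³ × (0.90/0.95)^12 = 4.18 (printed 4.20), and 4 of 19 gives 2⁴ × (0.90/0.95)^15 = 7.11. The two rows also overlap from 9 to 15. If the 20% in the text is used in place of the table, the 5%/5% figure of 78.9% becomes 73.6%.

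**The case against.** The strongest reply is that nothing operational is wrong. Alpha is correctly rounded, the power slip is under one point, and the decision is made by counting responses. A rule of two or more of 17 can only be one-sided, and the interval is there for estimation. Pairing a one-sided test with a two-sided 95% interval is common practice and not an error in itself. At the 25% alternative the awkward count makes up only 10% of rejections. All of this stands, and it is why the point is minor. It does not make 91% the power of the printed design, and it does not help the reader of a report with exactly 2 of 17.

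It may also be said that a 90% interval matches a one-sided 5% test, whereas the plan states 4%. That is true in general. Here the attainable p-values jump from 0.166 to 0.036, so the 90% interval and the rule agree in any case.

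Four stronger readings are tempting, and the documents do not support them:

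- **That alpha is misstated.** 3.6% is 4% to the nearest percent.
- **That 4%/91% were computed for 18 or 19 patients.** The same rule gives 3.9%/90.8% with 18 and 4.1%/91.2% with 19, but the 10+6 design in step 2 also rounds to 4%/91%. The origin cannot be identified.
- **That the real power is 79-82%.** This needs event rates of exactly 5%, where 11.4 says at most 5%, and it needs every stop counted as failure, which no section says. The 79% end also needs independent stops, although 11.4 ties delay to adverse events; if delays occur only in patients with those events, the delay rule adds nothing and the figure is 81.9%. It further depends on a delay table that conflicts with its own text.
- **That power should be judged at 20%, where it is 81.5%.** Section 3.3 says "it is anticipated PD-1 blockade will benefit 20-25% of patients with OCSCC", but benefit is not defined there as pathological response. Section 3.4 hypothesises 25-30% for the response endpoint.

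**Conclusion.** The point holds as a minor correction. For the printed rule, power is 90.2% against a stated 91%, an overstatement of about 0.8 points; alpha is fairly stated. These two figures rest only on the binomial model and the plan's own inputs. The design remains Simon-optimal for 4%/90%, so neither the 17 patients nor the decision rule is in question.

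The disagreement between test and interval is confined to exactly 2 of 17. It is a reporting inconsistency, not a flaw in the test.

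The stated power excludes the safety stops, and the plan should say so. With event rates of 2.5-5% and the assumptions of step 4, power including the stops is about 79-88% if every stop counts as not positive. It is about 87% at 5% if stopped trials with two responses already seen count as positive. None of these values is a property of the plan until it says how a stopped trial is analysed and the delay rule is reconciled.

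**What to change.** - **11.3.** Write: *Simon optimal two-stage design, one-sided alpha 4% (exact 3.6%) and power 90% (exact 90.2%) with 17 evaluable patients.* Add that this power is for the response rule alone and does not include the stops in 11.4.
- **11.2.1.** State that the test is one-sided. Report a two-stage-adjusted 90% interval beside the 95% interval, and note that at exactly 2 of 17 their lower limits are 2.4% and 1.6%. Say how a trial stopped for safety is analysed for efficacy.
- **11.4.** Reconcile the 10% and 20% figures and the overlapping rows of the delay rule. Only then, if power including the stops is wanted, give it as a range with its assumptions.

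The cost is protocol and SAP wording. No patients are added and the response decision rule is unchanged; the stated power becomes slightly less favourable.

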## 1 SCHEMA

## **2 OBJECTIVES**

### **2.1 PRIMARY OBJECTIVE**

To determine the pathological overall response rate (PR+CR) of neoadjuvant pre- surgical PD-1 inhibition in patients with surgically amenable oral cavity cancer.

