#### **OR**

Recurrent or persistent histologically proven locoregional OCSCC that was initially treated with surgery alone, and a clinically determined recurrent T-stage of 2-4 (based on AJCC Staging Manual v.7 guidelines).

**Note** – OCSCC includes the subsites of oral tongue, floor of mouth, gingiva, retromolar trigone, and buccal mucosa.

**Note** – To allow sufficient tumor tissue for the immunological analyses, patients with T-stage 1 OCSCC will be excluded

2. Greater than or equal to 18 years of age
3. ECOG performance status of 0 or 1
4. Screening labs must meet the following criteria and must be obtained within 14 days prior to registration:
  - WBC  $\geq 2,000/\mu\text{L}$
  - Absolute Neutrophil Count  $\geq 1,500/\mu\text{L}$
  - Platelets  $\geq 100 \times 10^3/\mu\text{L}$
  - Hemoglobin  $\geq 9.0 \text{ g/dL}$

- Serum creatinine  $\leq 1.5 \times \text{ULN}$  or  $\text{CrCl} \geq 40 \text{ mL/min}$  (if using the Cockcroft-Gault formula below):

$$\text{Female CrCl} = \frac{(140 - \text{age in years}) \times \text{weight in kg} \times 0.85}{72 \times \text{serum creatinine in mg/dL}}$$

$$\text{Male CrCl} = \frac{(140 - \text{age in years}) \times \text{weight in kg} \times 1.00}{72 \times \text{serum creatinine in mg/dL}}$$

- AST/ALT  $\leq 3 \times \text{ULN}$
- Total Bilirubin  $\leq 1.5 \times \text{ULN}$  (except subjects with Gilbert Syndrome, who can have total bilirubin  $< 3.0 \text{ mg/dL}$ )

5. Reproductive Status:

WOCBP must use appropriate method(s) of contraception. WOCBP should use an adequate method to avoid pregnancy for 23 weeks (30 days plus the time required for nivolumab to undergo five half-lives) after the last dose of investigational drug.

Men receiving nivolumab and who are sexually active with WOCBP will be instructed to adhere to contraception with a failure rate of less than 1% per year for a period of 31 weeks after the last dose of investigational product.

WOCBP is defined as any female who has experienced menarche and who has not undergone surgical sterilization (hysterectomy or bilateral oophorectomy) or who is not postmenopausal. Menopause is defined clinically as 12 consecutive months of amenorrhea in a woman over 45.

Women of childbearing potential must have a negative serum pregnancy test (minimum sensitivity 25 IU/L or equivalent units of HCG) within 24 hours prior to registration

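### Section 11.3 commits the trial to claiming a meaningful response in HNSCC from as few as 2 of 17 responders, but the rule tests only against 2% and enrols only OCSCC

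*Combined protocol and SAP*

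**What the plan says.** Section 11.3 describes a Simon two-stage design: nine patients first, stop if none responds, otherwise eight more. With two or more responders of 17 the sponsor will "reject the null hypothesis and conclude that treatment with Nivolumab results in a meaningful pathological response for patients with HNSCC".

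On rates, the same section says "With treatment, we anticipate a meaningful pathological response rate of 25" per cent and puts the untreated rate below 2%. Section 11.2.1 sets the null at 2% and the alternative at 25%. Section 3.4 adds "We hypothesize 25-30% overall response rate (PR+CR) in patients with OSCC".

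For the same cut-off, Section 11.2.1 stops at the test result: "If two or more patients among 17 evaluable patients respond, we will reject the null hypothesis". It also commits to estimation: "The clinical, radiographic and pathologic response rates will each be estimated with a 95% confidence interval, accounting for the two-stage design".

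On population, the primary objective (Section 2.1) concerns "patients with surgically amenable oral cavity cancer". Both routes into the trial in Section 4.1, newly diagnosed disease and recurrent or persistent disease, require OCSCC, and a note there limits the sites: "OCSCC includes the subsites of oral tongue, floor of mouth, gingiva, retromolar trigone, and buccal mucosa".

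**The concern.** The sentence in 11.3 turns a rejection of 2% into two further claims: that the response is meaningful, and that it holds for HNSCC. The test addresses neither. Because the wording is part of the pre-specified decision rule, a trial with two responders would carry that claim as its planned primary conclusion, and the estimate and interval printed beside it would not support it. A reader relying on the stated conclusion would take away more activity, in a wider population, than the data can show.

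**Working it through.** **Inputs.** Null 2% and alternative 25% (11.2.1, 11.3); stage 1 of 9 patients, stop at 0 responders; stage 2 of 8 patients; reject at 2 or more of 17 (11.3). Sidedness is not stated; a Simon design is one-sided, and I treat it so.

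**Formula.** The rule fails if there are 0 responders in 9, or exactly 1 in the first 9 and 0 in the next 8. With q = 1 − p:

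P(reject) = 1 − [q^9 + 9·p·q^8·q^8] = 1 − q^9 − 9·p·q^16.

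**Reproducing the plan's figures.**
- p = 0.02: 1 − 0.8337 − 0.1303 = 0.0360. The plan states alpha 4%.
- p = 0.25: 1 − 0.0751 − 0.0226 = 0.9024 (from unrounded terms). The plan states power 91%.

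An exhaustive search for alpha at most 5% and power at least 90% returns this same 9 + 8 design as optimal. The design stands.

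**What else meets the rule.**

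| True rate | P(2 or more of 17) |
|---|---|
| 2% | 3.6% |
| 5% | 17.2% |
| 10% | 44.6% |
| 15% | 66.8% |
| 25% | 90.2% |

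For example, at 10%: 1 − 0.3874 − 0.1668 = 0.4458. The probability reaches 50% at a true rate of 11.1%.

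**The smallest positive result.** 2/17 = 11.8%, less than half of 25%.
- Lower 95% limit, from P(continue and total ≥ 2) = 2.5%: 1.64%.
- Upper 95% limit: 38.5% if it solves P(stop or total ≤ 2) = 2.5%, or 34.7% if it solves P(continue and total ≥ 2) = 97.5%. The plan leaves the method to the cited Koyama and Chen approach, so I show both.

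Under either version the interval contains 25%, as well as rates far below it.

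**Population.** Section 2.1 names oral cavity cancer. Section 4.1 admits OCSCC only. Section 11.3 concludes for HNSCC. No patient with another head and neck site can enrol, so nothing in the data bears on the wider group.

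**The case against.** The best defence is that this is ordinary language for a Simon design. Such a rule screens for activity, and it has 90.2% power at 25%. Even the borderline result favours the alternative: exactly 2/17 has probability 108·p²·q^15, which is 9.0% at a true 25% and 3.2% at 2%, a ratio of about 2.8. The two-stage estimate, 95% interval and p-value are all planned, so a reader would see the uncertainty. HNSCC is used loosely elsewhere for these patients' own tumours (Sections 8.6 and 12), while the objective and eligibility are clear.

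Much of this stands. The rule is a sound screen, the intermediate power at 10% to 15% is normal for a 2% versus 25% design, and the planned interval limits the harm. It does not rescue the sentence. Support for some activity is not support for a meaningful rate, and loose labelling matters more in the primary conclusion than in a tissue-handling paragraph.

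Two stronger readings are tempting. A reader might infer that 25% is the plan's minimum meaningful rate, so that 2/17 falls short of a set bar. The text gives 25% as an anticipated rate described as meaningful; it sets no minimum. A reader might also infer that 11.2.1 contradicts 11.3. Both use the same null, cut-off and action; 11.2.1 is simply silent on meaningfulness.

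**Conclusion.** The point holds as a matter of the conclusion attached to the rule. Rejection supports a pathologic response rate above 2% in OCSCC. It does not by itself support a meaningful rate, because the only rate so described is 25% and a result of 2/17 is compatible with anything from about 1.6% to between 35% and 38%. It cannot support a statement about HNSCC generally.

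A reader might go on to infer that the cut-off or the error rates are wrong; the arithmetic shows they are not. At exactly 2/17 the two-sided 95% interval includes the 2% that the one-sided test has just rejected (p = 0.036). That might also be taken for a design fault. It is only the difference between a one-sided test and a two-sided interval, and it is gone at 3/17, where the lower limit is 3.91%.

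The figures assume exactly 17 evaluable patients, independent responses with a common rate, a one-sided test, and intervals from inverting the two-stage tail probability.

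**What to change.** In Section 11.3, replace the conclusion with wording such as: *With two or more responders among 17, the null is rejected and the conclusion is that the pathologic response rate in this OCSCC population exceeds 2%.* Add that whether the rate is meaningful will be judged from the two-stage estimate and 95% interval already planned in 11.2.1, read against the anticipated 25%. If wanted, a short note can say that at exactly 2/17 the two-sided interval will include 2% although the one-sided test rejects.

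This is a change of wording. Sample size, cut-off, endpoint, visits and analyses stay as they are. The price is a more modest claim for a borderline positive trial.
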